Randomized Prospective Clinical Analysis of Ultrasound-guided vs. Landmarkguided Biceps Corticosteroid Injections

PI: [name]

Co-investigators:

[name], MD, [name], MD

Introduction

Biceps tendinitis typically includes pain in the anterior shoulder that is reproduced with provocative maneuvers. Corticosteroid injections have been a mainstay of conservative management of biceps tendonitis. Many physicians have recently added ultrasound guidance to the injection to ensure accurate placement in the tendon sheath. Studies have shown that ultrasound guidance is more accurate than landmark guidance. However, the clinical significance of the accurate placement of the injection into the sheath is not clear.

Study Aim

Using randomization, prospectively determine superiority of either ultrasoundguided or landmark-guided biceps corticosteroid injections with regard to various clinical variables described at three weeks and three months.

Hypothesis

There will be a significant clinical difference in outcomes with ultrasound-guided being superior tolandmark-guided biceps corticosteroid injections at threeweeks and threemonth follow up.

Inclusion Criteria

Pain at intertubercular groove Anterior humeral pain Positive Speed's Test Bicep's tendinitis is primary diagnosis for patient Patient agrees to follow up and consent

Exclusion Criteria

Prior biceps surgery or injections Prior SLAP or labral repair Concomitant shoulder arthroplasty

Methods

Patients are diagnosed with biceps tendinitis in the outpatient clinic. After diagnosis, all the patients that meet inclusion/exclusion criteria will be offered to enroll in the study. Study will be described to the patient with regard to protocol and consent. All questions regarding the study will be answered, and it will be explicitly described that the

study involvement will not change clinical care. It will be explained that we expect a follow up appointment in three weeks and three months.

After collection of informed consent, the patient will be randomized to either ultrasound-guided or landmark-guided injection. The patient will complete clinical scores at the initial visit prior to the injection. After injection, the patient will have follow up scheduled for three weeks and three months. To ensure patient blinding, an ultrasound will be placed on the patient for both groups, but only active imaging with be performed for the ultrasound-guided patient group. For clinician blinding, a different clinician than the injecting clinician will perform the follow up examinations. The patient is instructed to not seek additional injections during the study.

Enrollment: 40-60 patients will be enrolled

Data collection will be performed as described below:

Pre-Procedural Data:

- Clinical Assessment Information (Symptomatic and asymptomatic side)
- Clinical Questionnaires
 - o Pain VAS
 - o ASES
 - o SST
 - o SANE
 - Biceps Specific Questions
 - o Fatigue pain
 - Anterior Shoulder Pain (0-10)
 - Presence of spasms
 - Provocative Maneuvers
 - o Tenderness at the bicipital groove with arm at neutral
 - O'Brien's, Speeds, Yergason's test

Post-Procedural Evaluation (same data as pre-operative visit)

- 3weeks
- 3 months

All data will be stored on a dedicated research computer on a local hard drive that requires password access, which only study personnel will possess. All patient identifying data will be removed and only demographic information will be included with an anonymous patient ID being ascribed. Statistical analysis will be performed in a blinded manner until results are final. These will include non-parametric comparison of groups with regard to all outcomes.

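### Does telling patients that taking part leaves their care unchanged, while randomizing technique and discouraging further injections, undermine the three-month comparison?

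*Protocol*

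**What the plan says.** All the relevant text is in the Methods section of the Protocol.

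- In the consent discussion, the study is to be described to the patient, all questions are to be answered, and the patient is to be told explicitly that "study involvement will not change clinical care".
- Allocation: "After collection of informed consent, the patient will be randomized to either ultrasound-guided or landmark-guided injection".
- Patient blinding: "an ultrasound will be placed on the patient for both groups", with active imaging in the ultrasound-guided group only.
- Clinician blinding: "a different clinician than the injecting clinician will perform the follow up examinations".
- Visits: "the patient will have follow up scheduled for three weeks and three months".
- Further treatment: "The patient is instructed to not seek additional injections during the study".
- Size: "40-60 patients will be enrolled".

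The Protocol does not say how a patient who nevertheless receives another injection is to be recorded or analysed.

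**The concern.** The consent sentence says that being in the study alters nothing, yet the study does alter several things. Chance, not clinician and patient, decides the technique. Landmark patients have an ultrasound placed on them that serves only the blinding. Someone other than the injecting clinician examines the patient at follow-up. Patients are asked to refrain from seeking more injections until the study ends.

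Two consequences might be feared.

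1. **Consent.** Patients could agree on the basis of a wrong account of what they give up.
2. **Estimate.** If care really is unchanged, a poor responder might have another injection before three months. If the instruction holds, that patient would not. The three-month difference would then describe either one injection alone or one injection plus whatever usual care adds. Should poor responders cluster in one arm and be injected again, the difference between arms would shrink. Three months is one of the two time points named in the Study Aim and Hypothesis, so this would matter if the text supported it.

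**Working it through.** **Step 1: set the consent sentence against each study procedure.** The Protocol states no figure on this point, so the main check is textual.

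| Study procedure | Conflict with the consent sentence, read literally? | Does it make the three-month outcome unclear? |
|---|---|---|
| Technique set by randomization | Yes | No; this is the comparison being made |
| Ultrasound placed in both groups | Yes, for landmark patients | No; it is the same step in both arms apart from active imaging |
| Different follow-up examiner | Slightly | No; it protects the assessment |
| Instruction on additional injections | Yes | Only if another statement allows them |

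**Step 2: look for a second rule on additional injections.** There is none. The consent sentence does not mention injections, and no other text permits or schedules them. The instruction quoted above is the only rule, it applies to both arms, and it covers the whole study. The reading in which further injections are allowed has to be inferred from a general sentence about care.

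**Step 3: check the milder reading of the consent sentence.** The Introduction describes corticosteroid injection as established conservative treatment and ultrasound guidance as something many physicians have added. Both arms therefore receive a treatment that the Protocol presents as already in clinical use. The sentence can be taken to mean that joining the study does not change the treatment on offer. This reading covers the randomized technique reasonably well. It does not cover the instruction on additional injections, which is given because the patient is in the study.

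**Step 4: size the feared dilution.** The Protocol gives no alpha, power, SD or target difference, so every input except the enrolment range is an assumption: two-sided 0.05, 80% power, equal allocation, a Mann-Whitney test with efficiency 3/π relative to the t-test, and normally distributed scores.

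- Effective size per arm = n × 3/π. For n = 20 this is 19.1; for n = 30 it is 28.6.
- Detectable difference, from the noncentral t distribution at those sizes: 0.93 SD at 20 per arm and 0.75 SD at 30 per arm.
- Dilution = (excess proportion re-injected in the landmark arm) × (gain per extra injection, in SD).

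With an assumed gain of 1 SD:

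| Excess re-injected | Dilution | Share of 0.75 SD | Share of 0.93 SD |
|---|---|---|---|
| 0% | 0 | 0% | 0% |
| 5% | 0.05 SD | 7% | 5% |
| 10% | 0.10 SD | 13% | 11% |
| 20% | 0.20 SD | 27% | 22% |

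**Step 5: ask what the consent wording contributes to those numbers.** The excess proportion is the difference between arms in patients who have another injection despite being told not to seek one. Neither factor in the product involves the consent sentence. Correcting that sentence while keeping the same instruction leaves every row of the table unchanged.

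**The case for a change.** The strongest case for acting is that what patients hear at consent is protocol content, which no SAP can repair. The sentence speaks of study involvement, so it cannot be reduced to a remark about the decision to enrol, and the instruction on injections plainly follows from involvement. The wording reaches all 40 to 60 patients and is cheap to correct. In addition, the listed follow-up data repeat the baseline items and include none for an extra injection, so an analyst might later lack the information to deal with one.

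Part of this stands. The sentence is loosely worded, and read literally it is inconsistent with the later Methods text; the two statements should say the same thing to the patient. The rest carries less weight. The same paragraph has the study described to the patient, which would cover randomization, the ultrasound placement and the instruction. The consent form is not among the material available, so no one can conclude from this text that patients are misinformed. Recording extra injections, and deciding how to analyse patients who have them, are matters commonly settled on the follow-up form and in the SAP. The SAP is not shown, so silence in the Protocol is not an error. A comparison of the groups as randomized remains a valid comparison of the two techniques even if some patients do have another injection.

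**Conclusion.** No change to the plan follows. What remains is a slip of wording: one summary sentence in the consent discussion is broader than the procedures that follow it, and it can be brought into line with them whenever the consent text is next edited. Reconciling the two would alter no estimate, no power figure and no source of bias.

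The claim that the three-month comparison is ambiguous does not hold, because the Protocol has a single rule on additional injections and states the groups, visits and outcomes clearly. The illustrative dilution runs from 0 to 0.20 SD as the assumed excess goes from 0% to 20%, with an assumed 1 SD gain per extra injection. It measures departure from the instruction and cannot be attributed to the consent sentence.

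This conclusion rests on two assumptions: that the consent discussion does describe the study procedures, as the Protocol requires, and that the handling of any extra injection is settled on the follow-up form or in the SAP.

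### Could the examiner-rated baseline signs be recorded by someone who already knows the arm, and would that bias the comparison?

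*Protocol*

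**What the plan says.** The relevant text is in the Methods section of the protocol and the data lists that follow it.

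- Allocation: "After collection of informed consent, the patient will be randomized to either ultrasound-guided or landmark-guided injection".
- Baseline questionnaires: "The patient will complete clinical scores at the initial visit prior to the injection".
- Baseline examination: the list headed Pre-Procedural Data includes "Tenderness at the bicipital groove with arm at neutral" and the O'Brien's, Speed's and Yergason's tests. The heading is the only statement of timing for these signs.
- Follow-up: the same items are collected again at three weeks and three months.
- Examiner blinding: "a different clinician than the injecting clinician will perform the follow up examinations". Nothing equivalent is said about the baseline examiner.
- Patient blinding: "an ultrasound will be placed on the patient for both groups", with active imaging in one group only.
- Before enrollment: "After diagnosis, all the patients that meet inclusion/exclusion criteria will be offered to enroll in the study". The Inclusion Criteria list "Pain at intertubercular groove Anterior humeral pain Positive Speed's Test".
- Analysis: non-parametric comparison of the groups on all outcomes. Neither change from baseline nor adjustment for baseline is mentioned.

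**The concern.** Read in the order written, the steps are consent, allocation, scores, injection. The injecting clinician must know the arm to give the injection, and no sentence stops that clinician from performing the baseline examination after allocation. Provocative tests involve judgment. An examiner who expects ultrasound guidance to do better, as the protocol's hypothesis does, might call borderline signs positive more readily in that arm. The arm would then start worse on paper and appear to improve more, even if the injections were equally effective. The protocol treats an examiner's knowledge of the arm as a risk at follow-up, so leaving the same signs unprotected at baseline looks inconsistent. At stake would be the validity of any change-from-baseline or baseline-adjusted comparison of these signs, and of the baseline table.

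**Working it through.** The protocol gives no figure to reproduce on this point. The check sets the passages side by side, and then adds an illustration of scale.

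**Which baseline items are exposed?**

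| Baseline item | Protection in the text | Exposure |
|---|---|---|
| Patient-completed scores and biceps questions | Probe placed in both groups, so the patient is blinded | Outside the concern |
| Speed's test | Must be positive for entry, which is settled before enrollment is offered | Little or none |
| Groove tenderness at neutral | Groove pain is an entry criterion, so tenderness is probably present in most patients | Small |
| O'Brien's and Yergason's tests | Not entry criteria, and timed only as pre-procedural | Open |

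**What has to happen for bias to arise?** All of the following are needed, and the protocol states none of them:

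1. The recorded baseline is a fresh examination after allocation, not the diagnostic one.
2. The examiner has been told the arm by then. The protocol does not say when, or to whom, the allocation is revealed.
3. Readings err systematically in one direction in one arm.
4. The analysis uses the baseline signs.

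If any link fails, the comparison between groups is unaffected.

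**Illustration of scale.** From the protocol: 40 to 60 patients. Assumed: equal arms, hence 20 to 30 per arm; one yes/no sign; no true difference between arms; true positivity at baseline/follow-up of 50/30, 60/30 or 70/40%; latent correlation of 0.3 or 0.5 between the two readings; two-sided Mann-Whitney test on change at 0.05; all misreading in one arm and one direction.

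If *k* of *n* patients in one arm are wrongly recorded as positive, that arm's mean change shifts by 100 × *k*/*n* points:

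- one patient: 100/30 = 3.3 to 100/20 = 5 points
- two patients: 200/30 = 6.7 to 200/20 = 10 points
- three patients: 300/30 = 10 to 300/20 = 15 points

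Simulated false-positive rates, 20,000 trials per setting:

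| Patients misread in one arm | Change from baseline | Follow-up values only |
|---|---|---|
| 0 | about 4 to 5% | about 4 to 6% |
| 1 | about 5 to 6% | same |
| 2 | about 7 to 9% | same |
| 3 | about 10 to 13% | same |

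The follow-up column cannot move with the number misread, because it does not use the baseline reading.

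**How much misreading is that?** With 50 to 70% truly positive, an arm holds between 0.3 × 20 = 6 and 0.5 × 30 = 15 truly negative patients. One misreading is 1/15 = 6.7% to 1/6 = 16.7% of them. Three are 3/15 = 20% to 3/6 = 50%. Nothing in the protocol suggests error on that scale, all in one direction.

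**The case for a change.** The strongest reply is that the order of allocation and examination is a matter of conduct. A statistical analysis plan can choose a method, but it cannot blind an examination that has already taken place. O'Brien's and Yergason's tests need not have been done before allocation, and with 20 to 30 patients per arm two or three slanted readings would show. Recording baseline first would use the same visit, staff and forms.

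Part of this stands. The protocol is silent on the order, and a baseline reading or baseline table made with knowledge of the arm cannot be re-blinded later. The objection goes too far if it implies that the comparison between groups is then beyond repair: an analyst can compare follow-up values, which are examined by a different clinician in blinded patients. The Study Aim is framed around results at three weeks and three months, which suits that analysis. How baseline enters the analysis is commonly left to the statistical analysis plan, which is not shown here. Silence on the sequence is also not an instruction to examine after unblinding.

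**Conclusion.** The concern is literally correct about the wording, but it identifies a missing detail and not a wrong rule. Randomizing after consent is ordinary practice, and a diagnostic examination already comes before the offer of enrollment. If that examination is the recorded baseline, which the protocol neither says nor rules out, there is no gap. A site that records the signs before the arm is revealed also complies fully with the text.

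The possible effect is confined to baseline-dependent comparisons of mainly three signs within a long outcome list. Its size cannot be derived from the documents. Under the assumptions above it is negligible for one misread patient and becomes material only with two or three misreadings in the same direction in one arm. This conclusion rests on the follow-up examinations and patient blinding working as described, and on the group comparison not depending on baseline readings taken with knowledge of the arm. On that footing the plan as written gives a sound comparison, and no change is called for.

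### Signs that entry does not require (O'Brien's, Yergason's, spasms) should be compared conditional on their pre-injection status, because an unrestricted comparison dilutes the difference between arms

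*Protocol*

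**What the plan says.** Under Inclusion Criteria, the protocol requires "Pain at intertubercular groove Anterior humeral pain Positive Speed's Test". O'Brien's test, Yergason's test and muscle spasms are not mentioned there.

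Under Methods, the pre-procedural data include "Presence of spasms" among the biceps-specific questions. The provocative maneuvers are groove tenderness on examination and "O'Brien's, Speeds, Yergason's test". The same items are collected again at three weeks and three months: "Post-Procedural Evaluation (same data as pre-operative visit").

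The final paragraph of Methods gives the analysis in one sentence: "These will include non-parametric comparison of groups with regard to all outcomes". It does not say whether follow-up status or change from baseline is compared, or whether a sign is analysed only in patients who had it. Enrollment is given as "40-60 patients will be enrolled", and no primary outcome is named.

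**The concern.** Every patient has a positive Speed's test at entry, so a negative test at follow-up means that the sign has gone. For O'Brien's, Yergason's and spasms, a negative finding at follow-up can mean either that the sign resolved or that it was never there. Patients who never had a sign cannot show its resolution, whichever technique they received. Including them without regard to baseline status therefore pulls the two arms together.

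Two things are at stake for these three signs. A real difference between techniques becomes harder to see. And in a trial this small, a chance difference in who had the sign before injection feeds straight into the follow-up comparison.

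**Working it through.** The protocol gives no sign prevalence, effect size, alpha or power, so it has no figure to reproduce. All rates below are assumptions, shown over a range. I assume 1:1 allocation (20-30 per arm from 40-60 in total) and a two-sided 5% test.

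**Dilution.** Let q be the share with the sign before injection, p_L and p_U the persistence rates among them (landmark, ultrasound), and r the rate of new signs among the rest, equal in both arms. The share with the sign at follow-up is q·p + (1 − q)·r in each arm, so the all-patient difference is q·(p_L − p_U). Comparing change from baseline gives the same factor q, because patients who never had the sign and stay negative have no change in either arm. For Speed's test q = 1, so it is not diluted.

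- Persistence 70% vs 35%: the 35-point difference becomes 0.7 × 35 = 24.5, 0.5 × 35 = 17.5 or 0.3 × 35 = 10.5 points.
- Persistence 60% vs 30%: the 30-point difference becomes 21, 15 or 9 points at the same prevalences, and 6 points at q = 20%.

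**Power, 70% vs 35%.** Simulation of 200,000 trials per setting, no new signs, number of baseline-positive patients random in each arm, pooled two-proportion z test. Each cell gives all patients vs baseline-positive patients only.

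| Prevalence q | 20 per arm | 30 per arm |
|---|---|---|
| 30% | 14% vs 23% | 20% vs 33% |
| 50% | 25% vs 36% | 34% vs 50% |
| 70% | 37% vs 48% | 50% vs 64% |

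At 30 per arm and q = 50%, Fisher's exact test gives about 25% vs 40%. A baseline-stratified test in all patients gives 48%.

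**Power, 60% vs 30%.** This is a formula calculation that fixes the number of baseline-positive patients at its expected value.

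- z test, 30 per arm: 17% vs 24% (q = 30%), 28% vs 37% (q = 50%), 42% vs 50% (q = 70%).
- Fisher's test, q = 50%: 19% vs 23% at 30 per arm, 12% vs 12% at 20 per arm.
- Fisher's test, q = 30%, 20 per arm: 6% vs 4%. With six patients per arm, the exact test is too coarse to gain from restriction.
- Enrolment for 80% power at q = 50%: 121 vs 84 per arm, both far above 20-30.

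**Chance imbalance.** At q = 50%, the arms differ by 20 points or more in baseline positivity with probability 27% (20 per arm) or about 15% (30 per arm). Suppose the techniques are equally effective and 70% of signs persist in both arms. A 20-point baseline imbalance then yields 0.20 × 70 = 14 points at follow-up, close to the 17.5 points expected from the assumed real effect.

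**The case against.** The strongest objection is that this is analysis-plan detail. The sentence on analysis says what the comparisons will include, not that they stop there. Baseline status is collected, and nothing rules out an analysis conditional on it. A statistical analysis plan that is not shown may already hold this. That stands in part: no data are lost, and the point improves the stated method rather than correcting an error. It remains worth making because the only method stated takes no account of a baseline value that is already recorded.

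A second objection is that the gain is modest. The affected signs are three among many outcomes with no named primary, and power stays low after the change. With Fisher's test in small subsets, the gain can vanish or reverse. This stands, and it makes the clearer meaning of the result at least as good a reason as power.

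A reader might also infer more than the document supports:

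- **That patients who never had a sign are counted as treatment successes, or that the signs are pooled.** The protocol defines no success or composite. If change is compared, these patients are simply unchanged.
- **That the comparison is biased.** Randomization balances these patients between arms on average. What remains is lost sensitivity and chance imbalance.
- **That groove tenderness is present in everyone at entry.** Entry requires pain at the groove, whereas the outcome is tenderness on examination in a stated arm position. The two may differ.
- **That maneuvers are scored only as positive or negative, so partial improvement is missed.** The protocol does not state how they are scored at follow-up. Asking for a graded score would be a preference.

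**Conclusion.** The point holds as a minor improvement to secondary items. O'Brien's, Yergason's and spasms are not guaranteed at entry, and the stated comparison does not use their pre-injection status. If it is run in all patients on follow-up status or change, the difference between arms shrinks by the factor q. That factor follows from arithmetic alone, provided new signs are equally frequent in both arms. How large the shrinkage is cannot be known, because the protocol gives no prevalence.

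Under the assumed 70% vs 35% persistence and 50% prevalence, the difference halves. With the z test, conditioning raises power from 25% to 36% at 20 per arm and from 34% to 50% at 30 per arm. The gain is smaller with a 30-point effect and depends on the test. Speed's test is unaffected.

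**What to change.** Add one or two sentences to the analysis paragraph. Each sign not guaranteed by the entry criteria should be analysed conditional on its recorded pre-injection status. This covers O'Brien's, Yergason's and spasms, and also groove tenderness on examination if not every patient has it at baseline. Fix one of two forms before the data are seen:

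- resolution among patients who had the sign before injection, with newly positive patients reported by arm; or
- a comparison in all patients, stratified by baseline status.

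Speed's test stays in all patients.

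No new data, visits or staff are needed, since the signs are already recorded before injection. The price is a smaller effective denominator. At 50% prevalence about 10-15 patients per arm inform each sign (0.5 × 20 to 0.5 × 30), and at 30% about 6-9. The results for these signs should therefore be presented as estimates with intervals and read as supportive only.

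### Does repeating the baseline data list at follow-up leave later injections, surgery and adverse events unrecorded?

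*Protocol*

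**What the plan says.** The Methods section introduces the data list with "Data collection will be performed as described below". Under Pre-Procedural Data, the list opens with "Clinical Assessment Information (Symptomatic and asymptomatic side" and does not say what that item contains. It then names the pain and function scores, the biceps-specific questions and the provocative maneuvers. For three weeks and three months the whole content is given by reference back: "Post-Procedural Evaluation (same data as pre-operative visit".

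Three other statements bear on the point:

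- On treatment after the study injection: "The patient is instructed to not seek additional injections during the study".
- On what is stored: "only demographic information will be included with an anonymous patient ID being ascribed".
- On what patients are told at consent: "study involvement will not change clinical care".

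Treatment is assigned as follows: "After collection of informed consent, the patient will be randomized to either ultrasound-guided or landmark-guided injection". The stated size is "40-60 patients will be enrolled". The planned analysis is a non-parametric comparison of the groups on all outcomes.

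**The concern.** A list drawn up for a visit before the injection has no obvious place for things that can happen only after it. Read literally, the follow-up visits would record pain, function and examination findings and nothing on what happened in between. The protocol itself treats further injections as relevant: it excludes patients with earlier ones and instructs participants not to seek more. Yet it names no item that would show whether the instruction was kept.

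Two things would be at stake. A three-month score might partly reflect a second injection or an operation, and a reader could not tell. The listed data would also give no count of harms by arm. A later analysis plan could repair neither, because it can work only with what was collected.

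A smaller point of wording sits beside this. Patients are told that taking part leaves their care as it is, while the study assigns the technique at random, places an ultrasound on patients in both groups for blinding and gives an instruction about further injections.

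**Working it through.** No figure in the protocol needs reproducing here, so the check is a count followed by a comparison of passages.

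**Count of named items** (Pre-Procedural Data):

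- Questionnaires: Pain VAS, ASES, SST, SANE = 4
- Biceps questions: fatigue pain, anterior shoulder pain, spasms = 3
- Groove tenderness = 1
- O'Brien's, Speed's, Yergason's = 3
- Total: 4 + 3 + 1 + 3 = 11

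Items among the 11 that ask about a further injection, surgery or an adverse event: 0. Items with no stated content: 1 (the clinical assessment item). The literal observation is therefore correct.

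**Is the list closed?** The sentence that introduces it says how data will be collected; it does not say that nothing else will be. The storage paragraph keeps demographic information that appears nowhere in the list, so the protocol already holds data beyond it. The clinical assessment item is repeated at both follow-up visits, and its content there is open. An account of treatment and complications since the last visit would fit within it. The layout of the list as available also leaves unclear whether this entry is a separate item or a heading. The absence of an explicit item is established; the absence of any record is not.

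**Is the rule itself wrong?** Measuring the same outcomes at baseline, three weeks and three months is what a comparison over time requires. The line does that job correctly.

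**What would the analysis lose?** The plan compares groups and states no exclusion or adjustment for further treatment. A comparison by assigned technique uses each patient's score whatever happened in between, so the result is the same whether or not a second injection was recorded. What a record adds is help in reading the result.

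**Can the loss be sized?** That would need the proportion of patients with a further injection, operation or adverse event in each arm, and the shift in score that follows. The protocol gives none of these, so no magnitude can be stated. Dividing one patient by 40 or by 60 would only restate the sample size.

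**The consent wording.** The Introduction describes corticosteroid injection as established treatment and ultrasound guidance as something many physicians now add. Both arms can thus be read as existing practice, and the statement to patients as saying that neither arm departs from it. The literal tension with the blinding step and the injection instruction remains, but it touches no data item or analysis.

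**The case for a change.** The best argument for a change is that the content of a visit is a protocol decision. It cannot be left to an analysis plan, and events of this kind are harder to recover once follow-up has ended. The protocol does specify the follow-up data, and it does so by copying a list written for a different moment. The remedy would also be cheap: two lines at each of two visits is 2 × 2 = 4 entries per patient, or 160 for 40 patients and 240 for 60.

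Part of this stands. No explicit item is listed, and recording further injections, surgery and adverse events is good practice, most plainly where patients have been told to avoid one of them. What does not stand is the step from not being named in a very short protocol to not being recorded. That step needs a closed list, and the text does not supply one. Low cost makes a suggestion reasonable; it does not show that anything stated is wrong.

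**Conclusion.** No change to the plan follows. The observation is accurate (0 of 11 named items) but describes detail left unwritten, not a faulty rule. A clinician seeing a patient three weeks or three months after an injection would ordinarily ask what has happened since. The undefined clinical assessment item gives the answer a place, and counts by arm can then be reported descriptively beside the comparison by assigned technique. That comparison is unaffected either way, and no effect on it can be quantified from the document. The consent sentence has a natural reading and no consequence for the data.

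This rests on two assumptions: that the data list is not meant to be exhaustive, which the unlisted demographic data support, and that forms or safety procedures not shown here may cover these events. If the sponsor intended the 11 named items to be everything recorded at follow-up, the gap in interpretation would be real, though the randomized comparison would still stand.
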